Autism spectrum disorder (ASD) is a range of complex neurodevelopment disorders characterized by social impairments, communication difficulties, and restricted, repetitive, and stereotyped patterns of behavior. Autistic disorder, sometimes called autism or classical ASD, is the most severe form of ASD, while other conditions along the spectrum include a milder form known as Asperger syndrome, and childhood disintegrative disorder and pervasive developmental disorder not otherwise specified (PDD-NOS).

Although ASD varies significantly in character and severity, it occurs in all ethnic and socioeconomic groups and affects every age group, with symptoms appearing before age 3. The Centers for Disease Control (CDC): Morbidity and Mortality Weekly Report, March 30, 2012 estimates that 1 out of 88 children age 8 will have an ASD, with males four times more likely to have an ASD than females.

Common Signs and Symptoms

The primary sign of ASD is impaired social interaction. As early as infancy, a baby with ASD may be unresponsive to people or focus intently on one item to the exclusion of others for long periods of time. A child with ASD may appear to develop normally and then withdraw and become indifferent to social engagement.

Children with an ASD may fail to respond to their names and often avoid eye contact with others. They have difficulty interpreting what others are thinking or feeling because they can't understand social cues, such as tone of voice or facial expressions, and they don't watch other people's faces for clues about appropriate behavior. They also lack empathy.

Many children with an ASD engage in repetitive movements such as rocking and twirling, or in self-abusive behavior such as biting or head-banging. They also tend to start speaking later than other children and may refer to themselves by name instead of "I" or "me." Children with an ASD don't know how to play interactively with other children. Some speak in a sing-song voice about a narrow range of favorite topics, with little regard for the interests of the person to whom they are speaking.

Children with characteristics of an ASD may have co-occurring conditions, including Fragile X syndrome (which causes mental retardation), tuberous sclerosis, epileptic seizures, Tourette syndrome, learning disabilities, and attention deficit disorder. About 20-30% of children with an ASD develop epilepsy by the time they reach adulthood.

Etiology

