Autism is a complex neurodevelopmental condition that is diagnosed based on three fundamental behavioral domains: aberrant social and communication interactions and specific behavioral patterns. Furthermore, symptom manifestation is variable among sufferers, ranging from a non-verbal child with mental retardation to high-functioning adults. Behavior patterns include hyperactivity, irritability, communication language deficits, and intellectual impairment. The majority of diagnosed cases of autism are idiopathic with an enigmatic pathogenesis, and as a result, therapeutic approaches have focused on mitigating specific symptoms rather than treating disease etiologies.

Therapeutic limitations derive from the disease's heterogeneity, which offers no lucid approach. Nevertheless, commonalities have emerged following extensive neuroimaging investigations. Magnetic resonance imaging (MRI) studies have demonstrated increased brain volume and head circumference during early developmental childhood, with the greatest pronouncement in infants and toddlers. This finding suggests that autistic brains experience a period a rapid overgrowth which hampers further development during later developmental stages. Morphological aberrations have been observed in the hippocampus, anterior cingulate cortex, prefrontal cortex, amygdala, and cerebellum. Another consistent observation has also been the reduction in cerebellar vermis volume, which helps to explain specific behavioral patterns in children.

Molecular analysis of postmortem brain tissue has revealed reduced Purkinje cell numbers, which helps to explain aberrant locomotive activity and level presser function. Another finding has been impaired neuronal connectivity within the cerebellum, amygdala, anterior cingulate cortex, and dorsolateral prefrontal cortex. As a consequence, synapse structure and function has demonstrated impairment in postmortem evaluations. Dendritic spines of glutamatergic neurons in autistic patients have shown morphological alterations and suppressed density, which, in turn, results in diminished synaptic transmissions. Nascent spines have been reported in frontal, temporal, and parietal cortices of autistic patients, and have a negative correlation with cognitive abilities in autism. Other neurological aberrations include signaling through metabotropic glutamate receptor (mGluR) and γ -aminobutyric acid (GABA)ergic system.

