low-level laser therapy (LLLTT). Operating under the auspices of photochemistry, LLLTT uses photonic energy to modulate the behavior and function of cells; this is accomplished by stimulating molecular entities capable of absorbing discrete wavelengths. For instance, cytochrome c oxidase (CCO), a terminal enzyme of the respiratory chain, contains a tetrapyrrole prosthetic group that has been shown to absorb 635nm. Photon-induced activation of CCO increases cell bioenergetics, which, in turn, activates intra-cellular secondary signaling cascades that in turn affect growth factor synthesis, cell proliferation, cytokine production, and expression of specific transcription factors. Studies have reported increased adenosine triphosphate (ATP) synthesis along with activation of the intracellular redox state following the production of reactive oxygen species (ROS). As an essential bio-catalyst, ATP lowers the activation for pivotal biochemical reactions within cells. Concerning neurons, laser irradiation has been shown to promote the recovery of injured peripheral nerves and the spinal cord. Moreover, studies have revealed that excitable cells like neurons can be directly stimulated by light, enhancing the action potential of the cell increasing the release of neurotransmitters such as glutamate and acetylcholine.

Influence of the intracellular redox state enables LLLTT to affect two well defined transcription factors, NF-κB and activator protein-1 (AP-1). The laser induced shift towards a more oxidized (alkalized) state impacts redox-sensitive transcription factors and subsequent gene expression. Recent evidence indicates that laser therapy is able to significantly diminish the expression of COX-2 by affecting the regulatory system controlling NF-κB, resulting in the reduction of inflammation. By suppressing the mechanism that upregulates inflammation, the application of laser irradiation can serve as a non-invasive means to down-regulate inflammatory agents reducing the severity of acne perhaps even preventing its onset.

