- 1) Repetitive Transcranial Magnetic Stimulation (rTMS): rTMS is a technique used in cognitive neuroscience research as well as in therapeutic approaches in certain neurological and psychiatry diseases to affect brain activity. It consists of applying a magnetic impulse to the brain through the scalp by placing an electromagnetic coil on the surface of the scalp. The electromagnetic coil produces high current pulses that induce an electrical field in the underlying brain tissue that is proposed to modify activity of those neurons inside the magnetic field and induce an electrophysiological change in the target area. When the induced field is above a certain threshold and is directed in an appropriate orientation relative to the brain's neuronal pathways, localized axonal depolarizations are believed to be produced, thus activating the neurons in the relevant brain structure.

Pilot studies evaluating application of rTMS to children and adolescents with both high functioning and low functioning autism have demonstrated reduction of repetitive behaviors and improved social functioning.

- 2) Transcranial Direct Current Stimulation (tDCS): tDCS has been evaluated through clinical trials for numerous neurological applications such as stroke, depression and schizophrenia, wherein its application has been shown to improve certain mental tasks and abilities. tDCS involves application of weak electric current to the brain through the surface of the scalp, such as through use of a 9 volt battery device.

Improvements in various cognitive functions have been consistently demonstrated. Regarding safety, only non-significant side effects have been reported, including a mild tingling and/or itching sensation under the electrode, fatigue after treatment, headache, and insomnia; all of which typically resolve without intervention within 72 hours.

- 3) Acupuncture and Acupressure: Acupressure involves the stimulation of specific acupoints by firm pressure, while acupuncture involves the insertion of very fine needles into the skin at specific acupoints that may be quickly inserted and removed or left in place for some period of time.

The therapeutic effect of acupuncture is based on stimulation at specific acupoints resulting in both local and distant effect via improving signal or modulation of electromagnetic energy

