Safety analyses will be completed on all subjects who were randomized to treatment group and received at least the first study treatment administration with the Erchonia® HLS Laser device.

Safety will be assessed by evaluating and comparing frequency and incidence of observed and/or reported adverse events between test and placebo treatment groups. A chi-square test with a continuity correction will be performed to compare the percentage of subjects who had adverse events and/or reactions between the test and placebo group subjects.

SAFETY AND CONFIDENTIALITY ISSUES

ADVERSE EVENTS

At any time throughout the study, any adverse event reported by a subject and/or subject's caregiver and/or observed by the study investigator will be recorded on the case report form and subsequently evaluated by the Principal Investigator for its relation to the study treatment and whether or not any corrective action need be taken. All applicable adverse events will be reported to the IRB.

Formal evaluation of the occurrence of any adverse events will take place at the end of each study treatment administration and each evaluation visit. In addition, subjects/caregivers will be instructed to contact the investigator at any other time that he or she believes a potential adverse event has occurred during the course of the subject's participation in the clinical study.

The investigator will record the observation or report of any adverse event and assign the relationship to the study treatment on the appropriate case report form in the subject's file and will report the occurrence to the governing IRB, if and as appropriate, within 5 days of the reported occurrence, or within 24 hours in the occurrence of a serious adverse event including death.

The only known potential adverse event associated with the use of laser devices is that long-term exposure to laser light could cause damage to eyesight. As a precaution, during all laser treatment administrations with the Erchonia® HLS at the test site, both the subject and the administration investigator will wear safety glasses that filter out the laser light spectrum. The administration investigator will wear KenTek Corporation KenTek C22-KMT-6101 light blue safety glasses and the subject will wear KenTek Corporation KGOG-6101 light blue Medium Goggles safety goggles. Additional information on this safety eyewear is contained above on pages 6-8 under the section titled: DEVICE SAFETY: RISK AND PREVENTION OF EYE INJURY.

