There are no other known potential adverse events from application of the study lasers. There have been no observed or reported adverse events or reactions to the application of the family of Erchonia® laser devices in several other studies using these laser devices. However, potential adverse events that may occur include, but are not necessarily limited to: skin irritation, skin discoloring, skin rash, skin indentations and infection. There may also be unknown or unanticipated risks to using the laser devices with this study treatment.

MONITORING OF THE CLINICAL STUDY

The study Monitor will assure that the investigator is executing the protocol as outlined and intended. This includes insuring that a signed informed consent form has been attained from each subject's caregiver prior to commencing the protocol, that the study procedure protocol is administered as specified, and that all study evaluations and measurements are taken using the specified methods and correctly and fully recorded on the appropriate clinical case report forms.

SUBJECT PRIVACY AND CONFIDENTIALITY

Records for each subject in the study will be maintained in separate files in a locked filing cabinet at the test site. The Principal Investigator will be responsible for ensuring that all records for a subject are stored in that subject's file at all times other than when information is being recorded on them.

Once a subject's participation in the study is complete and all of the required records are in the subject's file, copies of the documents may be made and supplied to the study Sponsor who will store them in a locked filing cabinet. Copies of subjects' case report forms will also be sent to Regulatory Insight, Inc. for the purpose of monitoring the data collection process and analysis of results. Regulatory Insight, Inc. will also maintain these copies in a separate clinical study file that is kept in a locked filing cabinet. The original records will be maintained at the test sites upon completion of the study in their original files and stored in a locked filing cabinet.

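### The adverse-event section names only eye, skin and infection risks although the rationale is neuronal stimulation, and the text available names no neurological, headache, sleep or fatigue symptoms to ask about

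*Combined protocol and SAP*

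**What the plan says.** All references are to the combined protocol and SAP.

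- **Risk statement** (Safety and Confidentiality Issues, Adverse Events): "The only known potential adverse event associated with the use of laser devices is that long-term exposure to laser light could cause damage to eyesight". The same section adds: "There are no other known potential adverse events from application of the study lasers". It then qualifies this: "potential adverse events that may occur include, but are not necessarily limited to: skin irritation, skin discoloring, skin rash, skin indentations and infection", and accepts that there may be unknown or unanticipated risks.
- **Rationale** (Theory of Mechanism of Operation): studies are cited as showing that "excitable cells like neurons can be directly stimulated by light, enhancing the action potential of the cell increasing the release of neurotransmitters". The section ends by proposing to place the laser along impaired regions of the brain, while calling the exact mechanism enigmatic.
- **Site of application** (Erchonia HLS Treatment Administration Protocol): the base of the brain and the temporal areas, from four inches away.
- **Comparator therapies** (Additional Supportive Information): several scalp therapies are said to share similar principles. For one of them, transcranial direct current stimulation, the reported side effects are "a mild tingling and/or itching sensation under the electrode, fatigue after treatment, headache, and insomnia".
- **Collection** (Adverse Events): any event reported by subject or caregiver, or seen by the investigator, goes on the case report form. There is a formal evaluation after every treatment and at every evaluation visit. The Principal Investigator judges the relation to treatment.
- **Analysis** (Safety Analyses): a continuity-corrected chi-square compares the percentage of subjects with adverse events or reactions between arms.

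**The concern.** The efficacy case places the action of the device in the brain, but the risk section names nothing neurological. It also omits the headache, fatigue and insomnia that the protocol itself reports for a therapy it offers as supportive.

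Two consequences follow. First, a caregiver or investigator who is given no named symptoms is less likely to look for them, and many of these children cannot volunteer them. Autism is described as "ranging from a non-verbal child with mental retardation to high-functioning adults", the diagnostic criteria in the Study Test Battery admit children with no spoken language, and the exclusion criteria rule out only a documented mental age below 18 months. Second, the protocol notes that "About 20-30% of children with an ASD develop epilepsy by the time they reach adulthood". An investigator told that only eye damage is a known risk has a ready alternative explanation for a seizure or staring spell.

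At stake are the completeness of the safety record for a device applied to children's heads, the relatedness grading, and reporting to the IRB, which the protocol limits to events judged applicable or appropriate.

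**Working it through.** The plan gives no adverse-event rate for this study and no capture rate, so there is no safety figure to reproduce. The main check is textual; the arithmetic only illustrates.

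**1. Is each kind of event named anywhere as a risk of this device?**

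- Eye damage: yes, as the known risk.
- Skin effects and infection: yes, in the open-ended list.
- Seizure or staring spell: no, although the rationale is neuronal stimulation.
- Headache, sleep change, fatigue: no, although headache, insomnia and fatigue are reported for a therapy called similar.
- Worsening behaviour: not listed as a risk, but measured by the ABC at baseline and Weeks 2, 4 and 8.

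**2. Does the stated collection rule fill the gap?** It covers every event that someone reports or observes. It does not say what to ask. Seizures, sleep loss and changed behaviour can be seen by a caregiver. Headache and fatigue in a non-verbal child must be inferred. No criteria for relatedness are given.

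**3. What would incomplete capture do to the planned test?** Input from the document: n = 20 per arm (Subject Sample Size). Assumptions: true rates of 40% active and 10% placebo, with the same capture fraction f in both arms. With a and b subjects with events, s = a + b and N = 40, the statistic is

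X² = N(|a(n − b) − b(n − a)| − N/2)² / [n² s (N − s)], significant above 3.841.

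Power is the sum of the binomial probabilities of all significant (a, b) pairs.

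- f = 1: 40% v 10%, difference 30 points, power 47.7%
- f = 0.6: 24% v 6%, difference 18 points, power 17.6%
- f = 0.4: 16% v 4%, difference 12 points, power 5.0%

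At assumed rates of 30% v 5%, power is 38%, 19% and 5% for f = 1, 0.75 and 0.5. The test is weak even with complete capture, because of the sample size; missed events weaken it further.

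**4. Would adding prompted events to that test help?** Prompting also brings in background complaints. With an independent background rate g in both arms, the any-event rate becomes 1 − (1 − p)(1 − g).

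- g = 0: 40% v 10%, power 48%
- g = 0.2: 52% v 28%, power 21%
- g = 0.4: 64% v 46%, power 11%

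Pooling prompted events into the any-event test would therefore do its own damage.

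**5. Would a seizure be unremarkable as background?** Assume the 20–30% epilepsy figure accrues at a constant hazard over 18 years: h = −ln(1 − 0.20)/18 = 1.24% per year, or −ln(1 − 0.30)/18 = 1.98% per year. The 8-week risk is 0.19–0.30% per child, so 0.08–0.12 cases are expected in 40 children, and the chance of at least one is 7–11%. The exclusion of active seizure disorders and treated epilepsy may put the true background lower. This says nothing about under-recording. It shows only that putting a seizure down to autism by default would not be justified.

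**The case against.** The protocol says no other *known* events exist, and a theoretical mechanism does not contradict that. The mechanism section reports general studies of neurons. The risk list is open, and unknown risks are admitted. A reader might infer that the protocol denies any neurological effect; it does not. This stands.

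A reader might also infer that such events *will* go unrecorded. The documents do not support that either. Every reported or observed event must be recorded, there is formal evaluation at each visit, and caregivers are told to make contact at any other time. The case report forms (Appendix C) are not in the text available, so a prompted list there cannot be ruled out. What remains is that the stated rule governs recording once an event has surfaced, not how it is brought to light.

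The CGI efficacy index, with four levels of side effects, is part of the CGI recorded at Weeks 2, 4 and 8. It is structured capture, but it names no symptoms and asks for a rating of treatment effect only, so it depends on the rater already suspecting the treatment.

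It might be thought that grading events unrelated would bias the arm comparison. It would not: the chi-square counts adverse events regardless of relatedness, and assessors are blinded. Attribution matters for relatedness tables and IRB reporting.

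The comparator is imperfect. The protocol says most of those therapies use direct contact and stronger energy, reports no safety issues with them, and ties the tingling and itching to an electrode. That is a reason to leave tingling and itching off the list, not to leave out headache, sleep change and fatigue. Finally, the pilot results are incomplete in the text available, so nothing can be said about whether the pilot reported an adverse-event count.

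**Conclusion.** The point holds in a limited form. The risk wording does not fit the protocol's own rationale, site of application and cited comparator. The text available names no symptoms to ask about and no criteria for relatedness. In children who may be non-verbal or of low mental age, headache and fatigue are liable to be missed, and neurological events are liable to be attributed to autism.

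The documents establish neither that this will happen nor how much would be lost. The power figures rest wholly on assumed event and capture rates and show direction only. The conclusion on prompting depends on what the case report form contains; the conclusion on wording does not. The change should be made because it is cheap and concerns safety data in children, not because a bias has been demonstrated.

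**What to change.** 1. In Adverse Events, remove the two statements that eye damage is the only known potential event and that no others are known. Name seizure or staring spell, headache or signs of head pain, sleep change and fatigue as plausible events, beside the existing eye and skin items. In Study Rationale, remove the description of the therapy as free of side effects.
2. Unless the case report form already does so, ask the caregiver about each named event, in identical words in both arms, at baseline and at each existing adverse-event evaluation. Count only events that are new or worse than baseline. Worsening behaviour need not be added, since the ABC measures it.
3. State that an event may not be judged unrelated merely because it is not a known laser effect.
4. Tabulate prompted events by type and arm, separately from the any-event chi-square. The separation is for analysis only: every event is still recorded and reported under the existing rules.

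The cost is about one form page, a few minutes per visit, and matching risk wording for caregivers. More minor events will be recorded in both arms, so the adverse-event tables will look less favourable. If the case report form already prompts for these events, item 2 falls away and the rest is wording and one table.
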